### 9.3 Variables

Vaccine safety will be assessed using diagnoses recorded in the KP utilization databases as a result of emergency, hospital, and outpatient clinic visits. Adverse events (AEs) will be collected via extraction of records from the KP utilization databases from 0 through 180 days post vaccination. Time periods when the subject is considered at risk after vaccination will depend upon the nature of the AE. The adverse events of interest and the time periods when the subject is considered at risk after vaccination are presented in [Table 9.3-1](#).

**Table 9.3-1 Summary of Planned Analyses**

Event of Interest	Period at Risk After Vaccination	Reference Period
Hypersensitivity MAEs a Seizures/convulsions MAEs a	0-3 days c	7-9 days d
Lower respiratory MAEs Wheezing MAEs Guillain-Barré syndrome MAEs a Bell's palsy MAEs a Encephalitis MAEs a Neuritis MAEs a Vasculitis MAEs a Any hospitalization Respiratory hospitalization b	1-42 days c (1-14 days and 15-42 days)	43-84 days
Narcolepsy/cataplexy MAEs a	1-180 days c	NA

MAE = medically attended event; NA = not applicable

a Narratives of each case will be included in the final clinical study report.

b A respiratory hospitalization will be defined by the ICD-9-CM codes sets for lower respiratory MAEs and wheezing MAEs.

c It is not possible to detect from clinical databases whether an event occurring on the day of vaccination began prior to or after administration of vaccine, although events of hypersensitivity or seizures/convulsions may occur just subsequent to vaccination but are unlikely to be recorded on the same day prior to vaccination. As a result, the period at risk after vaccination for events of hypersensitivity and seizures/convulsions begins on the day of vaccination (Day 0), and the period at risk after vaccination for all other events of interest begins 1 day after vaccination (Day 1).

d The reference period for the period at risk for 0 to 3 days was defined from 7 to 9 days to take into account cyclical variations that may occur during the same days of the week.

An MAE is defined as a coded medical diagnosis made by a health care provider and associated with a medical encounter (ie, visit to a medical clinic or emergency department, or a hospital admission). One or more MAEs could be assigned for a single encounter.

For MAEs of Guillain-Barre syndrome, Bell's palsy, encephalitis, neuritis, vasculitis, and narcolepsy/cataplexy, events will only be counted if the subject does not have a prior record of the event in the 12 months prior to vaccination (or index date for unvaccinated controls).

In addition, listings of any hospitalization within 180 days, any deaths throughout the entire study period, and exposed pregnancies throughout the entire study period will be provided.

A hospitalization is any medical event that results in inpatient hospitalization of any duration. In general, hospitalization signifies that the subject has been detained (usually involving at least an overnight stay) at the hospital or emergency ward for observation and/or treatment that would not have been appropriate in an outpatient setting. Hospitalization for elective surgery related to a pre-existing condition that did not increase in severity or frequency following initiation of the study need not be considered a hospitalization. If anything untoward is reported during an elective procedure, that occurrence will be captured as an MAE or hospitalization according to the usual criteria.

For analyses of any hospitalization and respiratory hospitalizations (see [Table 9.3-1](#)), only the primary discharge diagnosis will be analyzed.

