**4 CONTRAINDICATIONS**

**4.1 Severe Allergic Reactions**

Do not administer FluMist Quadrivalent to persons who have had a severe allergic reaction (e.g., anaphylaxis) to any component of the vaccine [see Description (11)] including egg protein, gentamicin, gelatin, and arginine, or after a previous dose of any influenza vaccine.

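### Hypersensitivity and seizures are counted from Day 0 with no prior-record rule, so pre-existing conditions coded on the vaccination day can bias the within-cohort and unvaccinated-control hazard ratios upward

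*Protocol*

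**What the plan says.** Protocol section 9.3 and Table 9.3-1 give hypersensitivity and seizures/convulsions a risk window of Days 0-3. They are the only outcomes whose window includes Day 0. Footnote c concedes that the databases cannot show whether an event on the vaccination day began before or after the dose. It includes Day 0 for these two outcomes because "events of hypersensitivity or seizures/convulsions may occur just subsequent to vaccination but are unlikely to be recorded on the same day prior to vaccination". Footnote d sets the comparator: "The reference period for the period at risk for 0 to 3 days was defined from 7 to 9 days".

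The event definition is broad: "An MAE is defined as a coded medical diagnosis made by a health care provider and associated with a medical encounter", and "One or more MAEs could be assigned for a single encounter". The restriction to a primary diagnosis in section 9.3 concerns hospitalizations only.

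A prior-record rule exists for some outcomes. "For MAEs of Guillain-Barre syndrome, Bell's palsy, encephalitis, neuritis, vasculitis, and narcolepsy/cataplexy" count only when the subject has no record of that event in the 12 months before vaccination or index date. Hypersensitivity and seizures are not on that list.

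Under section 9.1, unvaccinated controls are followed from the vaccination date of their reference recipient. No visit by the control is required on that date. Section 9.7.3 declares significance from the Cox hazard ratio. Section 9.9 states that limits on data validity should not systematically bias the association.

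**The concern.** Footnote c argues about the order of acute events within one day. A different kind of record is left open: a standing diagnosis, such as epilepsy or a known allergy, coded again at an encounter on the day of vaccination. Such a code meets the event definition, falls in the risk window, and is not removed by any prior-record rule.

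The problem is differential. Vaccination is given in routine care, so Day 0 brings the recipient into contact with the health system by design. Days 7-9 contain no such built-in contact, and neither does an unvaccinated control's assigned date. Old-condition codes can therefore add to the risk-window count without a counterpart on the other side. At stake is a false signal for two of the acute outcomes of most interest after a vaccine. Against inactivated vaccine, where both groups have a vaccination day, the concern is mainly dilution of a real effect.

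**Working it through.** The protocol attaches no figure to this choice. Its main quantitative claim, about 90% power for a relative risk of 1.5 at 1 in 100 with 10,000 children, reproduces at 88.9% (two-sided 0.05, equal groups assumed) and is not in dispute.

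**Inputs from the protocol.** Risk window of 4 days (0-3); reference window of 3 days (7-9); about 80,000 expected recipients (section 9.5).

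**Inputs assumed.** The protocol gives neither of these:
- b = background events per 1,000 persons per day, 0.05 to 0.2
- k = old-condition codes per 1,000 persons on the vaccination day, 0.1 to 0.5

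**Within-cohort, no true effect.** The risk-window rate is (4b + k)/4 per day and the reference rate is b, so the ratio is [(4b + k)/4]/b = 1 + k/(4b).

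| b | k | 1 + k/(4b) |
|---|---|---|
| 0.2 | 0.1 | 1.12 |
| 0.2 | 0.2 | 1.25 |
| 0.1 | 0.2 | 1.50 |
| 0.05 | 0.2 | 2.00 |
| 0.05 | 0.5 | 3.50 |

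**Versus unvaccinated controls, no true effect.** With the same b and no vaccination contact in controls, the ratio is (4b + k)/(4b), the same factor.

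**What it takes to cross the significance criterion.** Take 80,000 recipients, b = 0.05 and k = 0.2:
- Background events in Days 0-3: 80,000 × 4 × 0.05/1,000 = 16
- Old-condition codes on Day 0: 80,000 × 0.2/1,000 = 16, total 32
- Events in Days 7-9: 80,000 × 3 × 0.05/1,000 = 12
- Ratio: (32/4)/(12/3) = 2.0
- Standard error of the log ratio: √(1/32 + 1/12) = 0.339
- Lower 95% limit: exp(0.693 − 1.96 × 0.339) = 1.03

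On this normal approximation, sixteen codes among 80,000 people would meet the section 9.7.3 criterion for increased risk. With k = 0.2 but b = 0.1, the ratio is 1.5 and the lower limit 0.92, so the criterion is not met.

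**Versus inactivated vaccine.** With equal k in both groups and a true ratio R, the observed ratio is (4bR + k)/(4b + k). At R = 1 it is 1. At R = 2, b = 0.1 and k = 0.2 it is (0.8 + 0.2)/(0.4 + 0.2) = 1.67.

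**Do the planned safeguards remove these codes from the hazard ratio?**
- The Cox covariates and calendar-time structure (section 9.7.4) do not adjust for a contact tied to Day 0.
- The complementary analysis without high-risk subjects (section 9.9) relies on Annex 3, which lists neither epilepsy nor allergy.
- Analyses by setting (section 9.7.1) may show the pattern, but no rule acts on it.
- Narratives of each case are promised (footnote a), but nothing lets them change the count.
- The optional pre-vaccination reference models (section 9.7.4.1) keep the same Day 0 numerator.

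**The case against.** The strongest reply is that the mechanism depends on things the protocol does not show. The code sets for these two outcomes are not listed, and an acute-only set would remove most of the problem. Immunizations come from the tracking system and events from the utilization databases. Nothing says how often receiving the vaccine produces an encounter with coded diagnoses. Both points stand, and they limit what can be said about size.

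Omitting the prior-record rule from the primary count is also defensible. Seizures and allergic reactions recur, and a seizure after vaccination in someone with a recent seizure is a genuine safety event. This stands too and argues for a sensitivity analysis. The study is declared hypothesis generating, and further assessment may follow an observed increase. However, the protocol's warning concerns chance findings, and this one would be systematic.

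A reader might infer three stronger things that the documents do not support.

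- *A large bias is established.* Assume that all background seizure events are re-coding of chronic disease at 3 visits a year, and that 2%, 5% or 10% of affected subjects are coded at vaccination. The ratio would then be 1.6, 2.5 or 4.0. These inputs are not in the protocol and leave out incident seizures. If incident events merely equal that background, the excess halves, to 1.30, 1.76 and 2.52.
- *The inactivated-vaccine comparison hides a true hypersensitivity excess because allergic people are channelled to that vaccine.* The package insert says "Do not administer FluMist Quadrivalent to persons who have had a severe allergic reaction" to a component or after a previous influenza vaccine dose. No text says that such people receive inactivated vaccine instead, or that their allergy is coded that day.
- *Day 0 clinic codes should leave the primary count unless they come from a later encounter.* That needs an order of events within the day, which footnote c says the databases cannot give. It would also discard the immediate reactions that Day 0 is there to capture.

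**Conclusion.** The point holds as a gap in the outcome rule. Footnote c justifies Day 0 for acute events only, the prior-record rule skips the two outcomes that need Day 0, and no planned analysis takes old-condition codes out of the ratio on which significance is declared. The possible bias is upward in the within-cohort and unvaccinated-control comparisons, by a factor of 1 + k/(4b) when there is no true effect. Over the assumed ranges this runs from about 1.1 to 3.5; the protocol does not allow it to be narrowed. It would be smaller with acute-only code sets or with more incident events in the background. Against inactivated vaccine, equal coding gives no bias under the null and dilution otherwise; any further direction is conjecture. The section 9.9 statement that coding limits should not cause systematic bias is too broad for windows that contain Day 0. The design itself is not invalidated.

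**What to change.** Keep Days 0-3 as the primary window. Add to sections 9.3 and 9.7.3, for hypersensitivity and seizures/convulsions in all three comparisons, these prespecified sensitivity analyses:

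1. Days 1-3 only.
2. Only subjects with no record of the same event in the prior 12 months.
3. The hazard ratio after removing Day 0 cases that the planned narratives show to be pre-existing conditions, with the same review applied in every group.

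State that a significant hazard ratio that disappears in these analyses will be reported as possibly due to Day 0 coding. The first analysis also removes genuine immediate reactions, so it should be read together with the other two. Qualify the section 9.9 statement for windows that include Day 0, and carry the change into the matching table in the Abstract.

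The cost is a little more programming. The 12-month history is available because section 9.2.2 already requires 12 months of membership, and the narratives are already planned. The sensitivity analyses leave out some true Day 0 or recurrent events, but these stay in the primary count.

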## 9.7.3 Planned Analyses

Tabular summaries will be presented by treatment group. Categorical data will be summarized by the number and percentage of subjects in each category. Continuous variables will be summarized by descriptive statistics, including mean, standard deviation, median, minimum, and maximum. The age, gender, medical center, and prior year health care utilization level of the Q/LAIV and control groups will be summarized for descriptive purposes. Race information is not available in the Kaiser HMO databases.

Rates of events will be presented per 1,000 person-years. All statistical tests will be 2-sided and performed at the significance level of 0.05. Due to the exploratory nature of the study and the lack of formal hypothesis testing, multiple CIs will be constructed in the primary analysis without multiplicity adjustment. Due to the large number of unadjusted CIs to be evaluated, it is expected by chance alone that a number of CIs will not include one and suggest higher or lower event rates in the Q/LAIV group. Therefore, further statistical and medical assessments may be performed for events with observed increases that are statistically significant and/or medically important.

Incidence rates of adverse events of interest during periods at risk after Q/LAIV vaccination will be compared to incidence rates during reference periods later in the follow-up as presented in [Table 9.3-1](#) (within-cohort analysis) and to incidence rates in controls (matched unvaccinated subjects and matched IIV recipients).

Incidence rates will be reported as subjects with an event per 1,000 person-years. If a subject has more than one event in the analysis window, the subject will be counted only once for the analysis. Relative risks (RR) and corresponding 95% CIs will be constructed for each event for safety comparisons with control groups. Crude RR and adjusted hazard ratio (HR) and corresponding 95% CIs for each event will be derived:

- Crude RR and exact 95% CI will be calculated without adjustment of any covariate.
- Adjusted HR and corresponding 95% CI will be obtained using Cox proportional hazards model with calendar time data input adjusting for seasonal changes in

background rates and other confounders. This multivariable analysis is detailed in Section 9.7.4.

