#### 9.7.4 Multivariable Analysis

One of the primary challenges with performing safety assessment in this setting is that the background rates of many outcomes, such as respiratory events, change over time during the period of vaccination and follow-up. These changes in background rates are due to factors such as patterns in circulation of a variety of respiratory viruses and changes in exposure due to behavior influences such as the school year and holidays.

Controlling for seasonal changes in background rates that are dependent upon calendar time is important to minimize the potential seasonal bias and ensure that the effect of Q/LAIV on the rate of these events from a safety perspective, if any, can be accurately estimated.

The counting-process style of input for the Cox proportional hazards model can accomplish this by allowing the use of calendar time as the structure for defining the observation intervals ([Andersen and Gill, 1982](#)). Rows of observations for each subject will be generally structured as:

*pid, caldtst, caldtsp, event*

where *pid* is the subject identifier, *caldtst* is the calendar date of the beginning of the observation period, *caldtsp* is the calendar date of the end of the observation period, *event* is 1 if an event occurred at the end of the observation period, and 0 if an event did not occur, indicating censoring.

101,	11Oct2013,	22Nov2013,	0
102,	15Oct2013,	02Nov2013,	1

indicates that participant 101 was under observation from October 11 through November 22 and did not experience an event and was censored on November 22. Participant 102 was under observation from October 15 and experienced an event on November 02. Although not shown in this example, the values of main effects and covariates would also be included in each row.

This method controls for the effect of seasonal and other calendar time differences on background event rates because, when each component of the Cox partial likelihood is calculated at each event, the risk set includes only subjects who were under observation during the same calendar time period.

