#### **9.7.4.1 Within-cohort Analyses**

Within-cohort analyses will be conducted among Q/LAIV recipients to see if the incidence of safety outcomes is higher within an immediate post-vaccination “risk” period (eg, 0 to 3, 1 to 14, 15 to 42, and 1 to 42 days post vaccination) compared to later “reference” periods, ie, 7 to 9 days post vaccination for the risk period of 0 to 3 days, 43 to 84 days post vaccination for the risk periods of 1 to 14, 15 to 42, and 1 to 42 days.

This will be accomplished in the Cox models by evaluating the main effect of “period,” defined as a time-dependent variable using the counting-process style of data input. Covariates, stratification factors, and the calendar time structure will be incorporated to control for the effects of age, gender, level of health care utilization, and seasonal difference in background event rates. The main effect variable of “period” will compare post-vaccination “risk” periods to “reference” periods occurring after the risk period.

For each study subject, the beginning of each reference period will follow the end of the risk period.

For example:

*riskperiod03*: 1 = risk (Days 0 through 3)

0 = reference (Days 7 through 9)

*riskperiod142*: 1 = risk (Days 1 through 42)

0 = reference (Days 43 through 84)

If specific results from the primary analyses identify a statistically significant increased risk associated with Q/LAIV administration, additional models with main effects structured to compare the “risk” periods to “reference” periods occurring prior to vaccination may be constructed. To reduce the potential bias associated with the “healthy patient effect,” the reference period prior to vaccination would exclude the week immediately prior to vaccination.

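### The 7-9 day reference period matches only three of the four weekdays in the 0-3 day risk period, so the weekday control it was chosen for is incomplete in the unadjusted within-cohort analysis

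*Protocol*

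**What the plan says.** Table 9.3-1 in Section 9.3, and the same table in the abstract, give hypersensitivity and seizure/convulsion events a risk period of Days 0-3 and a reference period of Days 7-9. Footnote d offers one reason for the reference window: it "was defined from 7 to 9 days to take into account cyclical variations that may occur during the same days of the week". Section 9.7.4.1 repeats the pairing in the text, as "7 to 9 days post vaccination for the risk period of 0 to 3 days", and again in the coding of the variable riskperiod03. The window is therefore not a single typing slip.

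Section 9.7.3 fixes how the windows are used. Rates are per person-time: "Incidence rates will be reported as subjects with an event per 1,000 person-years". Two estimates are planned for each event. One is unadjusted: "Crude RR and exact 95% CI will be calculated without adjustment of any covariate". The other is a hazard ratio from a Cox model on calendar time. Significance is declared from the Cox model, and the exact unadjusted method replaces it if the Cox interval or p-value cannot be obtained. Section 9.7.4 explains that at each event "the risk set includes only subjects who were under observation during the same calendar time period".

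**The concern.** If a window is chosen to balance weekdays, each risk day needs a reference day exactly one week later. Here the fourth risk day has none. For someone vaccinated on a Thursday, the risk period runs Thursday to Sunday and the reference period Thursday to Saturday.

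Dividing by person-time corrects for four days against three. It does not correct for a different mix of weekdays. If medically attended events are recorded less often at weekends, an analysis with no other weekday control can show a rate ratio different from 1 when the vaccine has no effect. That matters for the crude estimates of two acute events, and for the decision itself if the exact fallback is used. Reference time is also a quarter shorter than full matching would give, which costs precision.

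**Working it through.** The protocol attaches no calculated figure to this window, and the power statements in Section 9.5 do not depend on it. The check is therefore of the window against its stated purpose.

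**1. Weekday pairing.** Inputs: risk Days 0-3 and reference Days 7-9 (Table 9.3-1, Section 9.7.4.1). Day d shares a weekday with day d + 7.

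| Risk day | Same-weekday day | In the reference period? |
|---|---|---|
| 0 | 7 | yes |
| 1 | 8 | yes |
| 2 | 9 | yes |
| 3 | 10 | no |

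Three of four weekdays are matched. Reference time is 3 days instead of 4, which is 25% less.

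**2. Size of the crude distortion with no vaccine effect.** The protocol gives neither weekend event rates nor the weekday distribution of vaccination, so both are assumed. Set the Monday-Friday rate to 1, Saturday to s and Sunday to u. Null crude RR = (mean daily rate over Days 0-3) / (mean daily rate over Days 7-9).

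Sums over the window by vaccination day:

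| Vaccinated | Risk, 4 days | Reference, 3 days |
|---|---|---|
| Mon | 4 | 3 |
| Tue | 4 | 3 |
| Wed | 3 + s | 3 |
| Thu | 2 + s + u | 2 + s |
| Fri | 2 + s + u | 1 + s + u |
| Total | 15 + 3s + 2u | 12 + 2s + u |

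Pooled over even Monday-Friday vaccination, RR = 3(15 + 3s + 2u) / [4(12 + 2s + u)].

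- s = 0.30, u = 0.25: 49.2 / 51.4 = 0.957
- s = 0.50, u = 0.40: 51.9 / 53.6 = 0.968
- s = 0.70, u = 0.60: 54.9 / 56.0 = 0.980

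Adding Saturday (risk 2 + s + u, reference 1 + s + u) and Sunday (risk 3 + u, reference 2 + u) gives totals of 20 + 4s + 4u and 15 + 3s + 3u. With even seven-day vaccination the RR is (5 + s + u) / (5 + s + u) = 1.00.

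The direction also depends on the assumption. If weekend rates were 1.5 times the weekday rate, the Monday-Friday figure would be 67.5 / 66.0 = 1.02.

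**3. With Days 7-10.** Numerator and denominator contain the same four weekdays for every subject, so the null crude RR is 1.00 for any weekly pattern and any mix of vaccination days.

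**4. Precision of the crude estimate.** Under a Poisson model, var(log RR) is proportional to 1/(4 × RR) + 1/(reference days). At RR = 1 the ratio is (1/4 + 1/3) / (1/4 + 1/4) = 7/6, so the standard error is √(7/6) = 1.08 times as large. At RR = 1.5 it is √[(1/6 + 1/3) / (1/6 + 1/4)] = √1.2 = 1.10 times.

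**The case against.** The strongest reply is that the analysis that decides significance is not affected. Its risk sets hold only people observed at the same calendar time, so risk and reference subjects are compared on the same weekday. This stands.

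Second, only one of the three comparisons uses the window. The matched analyses in Section 9.7.4.2 compare groups within the risk period, and unvaccinated controls are followed from the reference recipient's vaccination date. This stands too.

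Third, the fallback may rarely be needed, and the distortion may not change its result. The protocol gives no event rates from which to judge how often the Cox model would fail, with about 80,000 recipients expected. Suppose the fallback is used because one window is empty, and apply an exact conditional binomial test at one-sided 0.025. With every event in the risk window, significance needs 7 events: (4/7)^7 = 0.020, against (4/7)^6 = 0.035 for six. Building in a null RR of 0.96-0.98 gives about 0.018-0.019 at seven events, and seven are still needed. With every event in the reference window, five are needed either way. In these cases the artefact does not alter the decision.

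Fourth, the study is described as hypothesis-generating, every hypersensitivity and seizure case receives a narrative, and notable increases may be examined further. These lower the stakes.

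None of this explains why Day 10 is excluded or makes footnote d correct. The crude estimate has no weekday control other than the window. Section 9.7.3 plans it for each event, and nothing there excludes the within-cohort comparison, which the protocol's stated objective counts among its controls.

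**Conclusion.** The window does not fully meet its stated purpose and should be corrected, but this is not a serious threat to the study. The exposure is the within-cohort crude RR and exact interval for two event types, and the exact fallback if it is used. Under the assumed weekend rates and even Monday-Friday vaccination, the null crude RR is shifted by about 2-4%. With even seven-day vaccination there is no shift. The crude standard error is about 8% larger than necessary at RR = 1.

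A reader might infer more than the documents support:

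- **That weekday control fails altogether or the adjusted hazard ratio is biased.** Three of four days are matched, and the Cox model aligns calendar date.
- **That single-weekday figures describe the study.** At s = 0.5 and u = 0.4 the null RR is 0.875 for Wednesday, 0.87 for Thursday and 1.145 for Friday vaccinees. No analysis by vaccination weekday is planned, and these largely offset when pooled.
- **That four days against three is itself a bias.** Rates are per person-time, so unequal length alone costs only precision.
- **That the 8% applies to the hazard ratio.** It is a crude Poisson result. Information in the calendar-time model depends on how risk and reference subjects overlap on each date, which was not derived.

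**What to change.** Set the reference period for the 0-3 day risk period to Days 7-10 in Table 9.3-1 and its footnote d, in the abstract table and its footnote d, and in Section 9.7.4.1 (both the text and the coding, so that riskperiod03 = 0 means Days 7 through 10). Make the change before outcome data are examined.

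Records are already extracted for Days 0-180, so no new data are needed, and Day 10 still follows the end of the risk period as Section 9.7.4.1 requires. The one possible cost is a small loss of direct comparability with the earlier FluMist safety studies, if they used Days 7-9. The protocol does not state their windows.
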